#### 17.5.2. Safety Outcome 2: Incidence of air leak

This outcome will assess if there is a difference between the groups in the number of incidents of 'air leak' (pneumothorax and pneumomediastinum) occurring between randomisation and discharge from PICU.

#### 17.5.2.1. Derivation

The occurrence of any air leaks is recorded on the PICU Discharge/ Day 90 Status CRF and is indicated where the variable PDAIRLKC = "Yes" and the corresponding frequency of these events is expressed by the variable PDALINCI. All occurrences will be summed within patients.

#### 17.5.2.2. Analysis

A two-way table of the frequency of events of air leak per infants by allocated treatment group will be presented. The comparative analysis between arms will be as described in section 17.4.3.2.

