11.5 Analysis Plan

A full SAP will be written prior to the conduct of any comparative analysis of the treatment arms. The main features of the SAP are included here.

The primary analysis will be a test of the difference in geometric mean durations of MV between groups (placebo vs. poractant alfa), reported with the corresponding 95% confidence interval. The analysis will be conducted according to the intent-to-treat principle, and will incorporate the stratification factors of duration of ventilation (<24hrs and >=24hrs) prior to randomisation and site.

For the secondary outcomes, longitudinal data for VI, OI, OSI and SF will be analysed with joint modelling. LRSQ data will be modelled longitudinally and comparisons made between groups. Binary data will be reported in terms of relative risk with 95% confidence intervals.

Within BESS, data will be collected as to ascertain readiness for spontaneous breathing test and time of extubation.

As much information as possible will be collected about the reasons for missing outcome data; this will be used to inform any imputation approaches employed in the analysis. Such methods will be fully described in the SAP.

IRAS 220853 Page **63** of **87**

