# 12. Confidence Intervals, p-values and Multiplicity

Confidence intervals will be reported for all point estimates at the 95% level. Baseline summaries will be presented to 1 decimal place whilst all other values will be reported to 2 decimal places, or 1

significant figure if it would round to zero at 2 decimal places, and all p-values will be reported to 3 decimal places. There are no planned adjustments for multiplicity.

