#### 17.4.3.2. Analysis

A two-way table will be presented with the frequency of interventions received vs allocated treatment. A Chi-squared test for trend will be used to test for an association between allocation and the number of trial interventions if the expected cell frequencies are greater than five and Fisher's exact test will be used if they are not. The Chi-squared test statistic and corresponding p-value will be presented for the test.

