#### 17.4.6.2. Analysis

This binary outcome will be presented in a two-way frequency table (allocated treatment group by use of steroids during extubation) and a Chi-squared test will be used to test association between allocation and use of steroids if the expected cell counts a greater than five and Fisher's exact test will be used if they are not. The Chi-squared test statistic and corresponding p-value will be presented for the test.

The relative risk between arms of having to use steroids during extubation will be presented along with 95% confidence interval.

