#### 17.5.1.2. Analysis

The total number of occurrences of failure to administer intervention due to adverse event will be presented overall and for both treatment groups and also the number of patients in each group will be reported.

A two-way table of the frequency failed intervention delivery per infants by allocated treatment group will be presented. The comparative analysis between arms will be as described in section 17.4.3.2.

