#### 17.5.3.2. Analysis

A two-way table of the frequency of parent reported readmission to hospital by allocated treatment group will be presented. The comparative analysis between arms will be as described in section 17.4.3.2.

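### Failed administration, air leak and readmission are compared by a test and p-value only, with no effect estimate or confidence interval

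*SAP*

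**What the plan says.** SAP 17.5.1.2 (failed administration), 17.5.2.2 (air leak) and 17.5.3.2 (readmission) have the same structure. Each gives a table by arm, for example "A two-way table of the frequency failed intervention delivery per infants by allocated treatment group will be presented" and "A two-way table of the frequency of parent reported readmission to hospital by allocated treatment group will be presented". Each then hands over the comparison: "The comparative analysis between arms will be as described in section 17.4.3.2".

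Section 17.4.3.2 was written for the number of doses received. It reads: "A Chi-squared test for trend will be used to test for an association between allocation and the number of trial interventions", with Fisher's exact test when expected counts are not above five. Its stated output is: "The Chi-squared test statistic and corresponding p-value will be presented for the test". It names no effect measure and no interval.

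The other safety outcomes in SAP 17.5 (tube replacement, death in PICU, later mortality to day 90) are sent to 17.4.6.2, the steroid-use section, which adds an estimate: "The relative risk between arms of having to use steroids during extubation will be presented along with 95% confidence interval".

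Two general statements bear on this. Protocol 11.5: "Binary data will be reported in terms of relative risk with 95% confidence intervals". SAP 12: "Confidence intervals will be reported for all point estimates at the 95% level".

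**The concern.** For uncommon harms in a trial not sized to detect them, a non-significant test is the likely result whether or not there is an excess. What informs the reader is the estimate and its interval, because the upper limit shows how large an excess the data have not ruled out. For these three outcomes the plan pre-specifies neither. If Fisher's test is used, there is not even a chi-squared statistic to report, so the comparison is a single p-value.

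The SAP already applies the fuller method to tube replacement and deaths and gives no reason for treating these three differently. SAP 12 does not close the gap: it attaches intervals to point estimates, and 17.4.3.2 defines no point estimate.

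**Working it through.** **1. The plan's own figure.** The only sizing for the main trial (Protocol 11.3) is for ventilation time: means 4.83 and 4.08 days, SD 2.5, two-sided 5%. With k = SD/mean, the log-scale variances are ln(1 + 0.518²) = 0.237 and ln(1 + 0.613²) = 0.319. The log-scale difference is ln(4.08/4.83) − 0.5 × (0.319 − 0.237) = −0.209. Then n = (z_α + z_β)² × (0.237 + 0.319) / 0.209², which gives, unrounded, 99.5 (80% power) and 133.2 (90% power), so 100 and 134 per group as stated. 134/0.95 rounds up to 142, or 284 in total. The figure reproduces. No power or precision is stated for any safety outcome.

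**2. What an interval would add.** The documents give no rates for the three outcomes, so every count below is an assumption. Inputs: 142 infants per arm, all observed, each scored as any event or none.

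- Relative risk: RR = (a/142)/(b/142).
- Standard error of ln RR: √(1/a − 1/142 + 1/b − 1/142).
- 95% CI: RR × exp(±1.96 × SE).

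For 6 v 2: SE = √(0.1667 + 0.5 − 0.0141) = 0.808 and exp(1.96 × 0.808) = 4.87. The interval is 3.0/4.87 = 0.62 to 3.0 × 4.87 = 14.6. The risk difference is 4/142 = 2.8 percentage points, with simple (Wald) 95% CI −1.0 to 6.7.

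| Infants with ≥1 event | Expected events per arm | Fisher p | RR (95% CI) |
|---|---|---|---|
| 6 v 2 | 4 | 0.28 | 3.0 (0.62 to 14.6) |
| 8 v 4 | 6 | 0.38 | 2.0 (0.62 to 6.5) |
| 12 v 6 | 9 | 0.22 | 2.0 (0.77 to 5.2) |
| 30 v 20 | 25 | 0.16 | 1.5 (0.90 to 2.5) |

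In a two-by-two table the SAP's rule would select Fisher's test for the first row and the chi-squared test for the others. With χ² = 284 × (a(142 − b) − b(142 − a))² / (142² × (a + b) × (284 − a − b)), those three give χ² = 1.39, 2.14 and 2.43, so p = 0.24, 0.14 and 0.12. None is significant under either test. The upper limits run from 2.5 to 14.6, and the p-values do not convey that.

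**3. How often a real excess would be missed.** This is the power of Fisher's test at 142 per arm, found by enumerating all pairs of binomial counts under assumed rates:

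- 2% v 4%: 8%
- 5% v 10%: 28%
- 10% v 20%: 60%

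Applying the SAP's switch to the chi-squared test when expected counts exceed five raises these to 11%, 35% and 67%. For an uncommon event (assumed 2% or 5%), a true doubling would usually give a non-significant result.

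**The case against.** Several points on the other side are fair.

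- **Counts, not binary data.** SAP 17.5.2.1 sums air leaks within patients, readmission is recorded from zero up to six or more, and failed administration can recur over three doses. Protocol 11.5 speaks only of binary data. A reader might infer a plain breach of the protocol, but the text does not go that far: the conflict appears only when each outcome is read as any versus none. That reading is reasonable, since air leak has a Yes/No variable and SAP 17.5.1.2 also reports the number of patients affected. It is still a reading. If the count scale is kept, the gap remains, because a count comparison also needs an estimate, such as a rate ratio.
- **Reporting as no difference.** A reader might infer that a non-significant result will be presented as showing no harm. Neither document says so. It is a risk when the p-value is the only comparative result, not a stated intention.
- **Which outcomes are affected.** A reader might infer that the outcomes nearest to procedural harm were the ones left out. That does not hold. Readmission is all-cause and runs to 90 days. Tube replacement is arguably nearer, given that Protocol 3.4.2 lists tube blockage among the reactions to poractant alfa, and it does get a relative risk.
- **The data are visible.** All three outcomes are tabulated by arm, so a reader could compute a crude ratio. This limits the damage but does not supply a pre-specified estimate. The adverse event tables in SAP 20 do not supply one either: they are descriptive and group infants by treatment received.
- **Test and interval agree.** Every interval in the illustration includes 1, so adding it reverses no conclusion. What it adds is the size of excess still compatible with the data.

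**Conclusion.** The point holds as a gap in safety reporting. Three of the outcomes in SAP 17.5 have a p-value-only comparison, while tube replacement and deaths have an estimate with an interval. The shortfall against Protocol 11.5 is conditional on the any-versus-none reading. It also rests on the available protocol, version 2.0, whereas SAP 5 cites version 3.0.

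The primary analysis is unaffected. The size of the problem is illustrative only: the counts and rates are assumed, and 142 per arm takes every infant as observed. Readmission depends on parents returning a questionnaire, so its denominators may be smaller and its intervals wider. Within those assumptions, 2 to 6 affected control infants and a two- to threefold excess leave upper limits for the relative risk of about 5 to 15. The change is worth making because the method is already in the SAP and the data are already collected.

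**What to change.** In SAP 17.5.1.2, 17.5.2.2 and 17.5.3.2:

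1. Report, per arm, the number of infants with at least one event, using infants with the outcome observed as the denominator.
2. Report the relative risk with 95% CI as in 17.4.6.2, plus the risk difference with 95% CI. Use exact methods when cells are sparse. When an arm has no events the simple relative risk and its log-method interval break down, so the exact risk-difference interval should carry the result.
3. Keep the count-per-infant tables, so that recurrence is not lost. Add a rate ratio with 95% CI if recurrent events are common enough to matter.
4. State that a non-significant p-value for these outcomes is not evidence of no harm.

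The cost is a few lines of SAP wording and code, with no new data collection and no effect on sample size or the primary analysis.

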#### 17.5.3. Safety Outcome 3: Parent reported readmission to hospital

Parent reported readmission to hospital (all causes) up to 90 days post randomisation

#### 17.5.3.1. Derivation

The outcome is captured on JotForm Form 1 90-day Readmission and the frequency is captured in the column: "How many times was your child admitted to hospital in the 3 months after they took part in BESS?" and can take values from zero to six or more.

#### 17.5.3.2. Analysis

A two-way table of the frequency of parent reported readmission to hospital by allocated treatment group will be presented. The comparative analysis between arms will be as described in section 17.4.3.2.

#### 17.5.4. Safety Outcome 4: Any need to replace the endotracheal tube

This outcome will assess if there is a difference in the frequency of the need to replace the endotracheal tube (ET) between randomisation and successful extubation.

# 17.5.4.1. Derivation

The details for whether the ET tube needs to be replaced can be found on the Observations and Outcomes CRF indicated where the variable OAOCETTC = "Yes".

#### 17.5.4.2. Analysis

This outcome will be analysed as described in section 17.4.6.2, the two-way table will be allocated treatment group by replacement of ET tube required and the relative risk will be of the tube having to be replaced.

#### 17.5.5. Safety Outcome 5: Death during PICU admission

This outcome will assess if there is a difference in the occurrence of death from randomisation to PICU discharge.

#### 17.5.5.1. Derivation

Death during PICU admission and all-cause mortality at 90 days after randomisation will be recorded on the Day 90 Status CRF indicated when the variable DNBTBAC = "No". All-cause mortality at Day 90 will be established via a local enquiry against the hospital electronic health record and will be recorded on the Day 90 status CRF.

This variable DNBTBAC (is the infant believed to be still alive?) will be marked as "No" whether the death occurred in the PICU or at any point up to the completion of the 90 days status CRF (including during any hospital admission following PICU admission). To establish if the death occurred during PICU stay, the PICU discharge CRF will be cross checked and if the date/ time of PICU discharge (PDA90DTD) is not completed then the death will be assumed to have occurred during PICU stay and if it is complete then the death will be assumed to have occurred either in hospital or following discharge from hospital up to day 90 post randomisation.

#### 17.5.5.2. Analysis

This outcome will be analysed as described in section 17.4.6.2, the two-way table will be allocated treatment group by whether the infant died during PICU (which will be established as described in section 17.5.5.1) and the relative risk will be of death occurring.

#### 17.5.6. Safety Outcome 6: All-cause mortality

This outcome is to assess if there is a difference in all-cause mortality at 90 days post randomisation between arms. This outcome will be assessed from PICU discharge to 90 days post randomisation.

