3.6.2 Secondary Outcomes/Endpoints

The secondary outcome measures for the trial (WP-A) are:

For efficacy:

- 1. duration of post-extubation non-invasive respiratory support (all forms of non-invasive ventilation: e.g. nasal CPAP and nasal high low oxygen)
- 2. duration of oxygen supplementation
- 3. number of trial interventions given (both poractant and placebo)
- 4. use of steroids to assist extubation
- 5. duration of stay on PICU and in hospital;
- 6. change over time from baseline of Ventilation Index (VI), Oxygenation Index (OI) and Oxygenation Saturation Index (OSI) while mechanically ventilated, & SpO₂/FiO₂ (SF) ratio.¹
- the score (value) of parent reported outcome measure of respiratory symptoms the "Liverpool Respiratory Symptom Questionnaire" (LRSQ) at 6m (+/-1m) and 12m (+/-1m) (20);

IRAS 220853 Page **20** of **87**

¹ VI and OI are validated physiological measurements reflecting respiratory function (gas exchange) normalised for level of respiratory support provided by MV, but require blood sampling(21). OSI is a validated physiological measurement reflecting respiratory function (gas exchange) normalised for level of respiratory support provided by MV that does not require blood sampling (41). The SF ratio is a non-invasive measure of respiratory function and can be calculated in situations where invasive blood gas monitoring and MV has ceased (22).

8. time from randomisation to meeting study criteria for readiness for Spontaneous Breathing Test

For safety:

- 1. failure to administer the intervention due to any adverse event during preparatory processes (tracheal toilet or BAL)
- 2. failure to complete administration of the intervention due to any adverse event during administration of the intervention (regardless of which arm of allocation)
- 3. incidents of 'air leak' (pneumothorax and pneumomediastinum) occurring before discharge from PICU
- 4. other adverse events and serious adverse events associated with the intervention
- 5. any need to replace the endotracheal tube
- 6. parent reported readmission to hospital (all causes) up to 90 days post randomisation
- 7. death during PICU admission
- 8. all-cause mortality at 90 days post randomisation

IRAS 220853 Page **21** of **87**

Table 1: Objectives and Outcome Measures

Objectives	Outcome Measures	Timepoint(s) of evaluation of this outcome measure (if applicable)

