	Parent reported readmission to hospital (all causes) up to 90 days post randomisation	PICU discharge to 90 days post-randomisation
	Death during PICU admission	Randomisation to PICU discharge
	All-cause mortality at 90 days post randomisation	PICU discharge to 90 days post-randomisation

IRAS 220853 Page **23** of **87**

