## 9.2. Secondary outcomes

- Time from randomisation to meeting criteria for readiness for spontaneous breathing test (SBT)
- Number of trial interventions given
- Change from baseline of ventilation index, oxygenation index, and oxygenation saturation index whilst on MV
- Change from baseline of SpO2/FiO2 (SF) ratio
- Duration of oxygen supplementation
- Use of steroids to assist extubation
- Duration of post-extubation non-invasive respiratory support
- Duration of stay at Paediatric Intensive Care Unit (PICU) and in hospital
- Failure to administer intervention due to any adverse event (AE) during preparatory processes
- Failure to complete administration of intervention due to any AE during administration of intervention
- Incidence of pneumothorax or pneumomediastinum before discharge from PICU
- Any need to replace the endotracheal tube
- Parent-reported readmission to hospital
- Death during PICU admission
- All-cause mortality at 90 days post-randomisation
- Liverpool Respiratory Symptom Questionnaire (LRSQ) score

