#### 17.4.8.1. Derivation

The duration of stay at PICU will be calculated by taking the difference between the date/ time of randomisation taken from the Almac randomisation log and the date/ time of discharge from PICU (PDAISDTD) on the PICU Discharge CRF or the date of death (DNBDIDD) Day 90 Status CRF if the death occurred before PICU discharge. This can be expressed as:

 $T(PICU) = \begin{cases} PDAISDTD, & if dicharged \\ DNBDIDD, & if death occurs in PICU - T_{RAND} \end{cases}$ 

The overall duration of stay in hospital (including both time in PICU and time in hospital) will be calculated by taking the difference between the date/ time of randomisation taken from the Almac randomisation log on and the date/ time of hospital discharge (PDA90DTD) on the PICU or the date of

<sup>4 If date and time of death is required to calculate time in hospital or time in PICU then this will be estimated at 12:00 as death is only recorded as date.

death (DNBDIDD) Day 90 Status CRF if death occurred before hospital discharge. This can be expressed as:

 $T(Hospital) = \begin{cases} PDA90DTD, & if dicharged \\ DNBDIDD, & if death occurs \end{cases} - T_{RAND}$ 

Note that if death occurs during PICU then T(Hospital) = 0.

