#### 17.5.6.2. Analysis

This outcome will be analysed as describe in section 17.4.6.2, the two-way table will be allocated treatment group by whether the infant died during after PICU stay and before 90 days post randomisation (which will be established as described in section 17.5.5.1) and the relative risk will be of death occurring.

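### The outcome named 90-day all-cause mortality counts only deaths after PICU discharge, so total 90-day mortality by arm is never produced; the SAP also gives the variable that places a death in PICU two conflicting labels

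*SAP*

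**What the plan says.** **The outcome as listed.** Protocol 3.6.2 lists "all-cause mortality at 90 days post randomisation" among the safety outcomes, and SAP 9.2 lists "All-cause mortality at 90 days post-randomisation". Neither list restricts where, or after what event, the death must occur.

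**The outcome as analysed.** SAP 17.5.6 opens with the same 90-day outcome and then adds: "This outcome will be assessed from PICU discharge to 90 days post randomisation". SAP 17.5.6.2 builds the two-way table on "whether the infant died during after PICU stay and before 90 days post randomisation". Protocol Table 1 gives the all-cause mortality row the window "PICU discharge to 90 days post-randomisation".

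**Deaths in PICU.** Safety Outcome 5 (SAP 17.5.5) covers randomisation to PICU discharge, with its own two-way table, test and relative risk.

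**How a death is placed.** SAP 17.5.5.1 takes vital status from DNBTBAC, which records deaths both in PICU and later. It then says that "if the date/ time of PICU discharge (PDA90DTD) is not completed then the death will be assumed to have occurred during PICU stay". SAP 17.4.8.1, deriving length of stay, attaches the same variable name to the "date/ time of hospital discharge (PDA90DTD)" and uses PDAISDTD for PICU discharge. It takes the date of death from DNBDIDD.

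**The concern.** A statistician who programs SAP 17.5.6 exactly as written would produce a result headed 90-day all-cause mortality that leaves out every death in PICU. The trial gives an endotracheal drug to ventilated infants, so the omitted deaths are those closest in time to treatment. SAP section 5 says that the analysis report will support the EudraCT posting and the primary publications, so a post-PICU count could be published under the all-cause label.

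The SAP also does not say what happens to infants who died in PICU when the table for Safety Outcome 6 is drawn up. Depending on the choice, the result is either mislabelled or restricted to a group selected after randomisation.

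The split between Safety Outcomes 5 and 6 depends on one discharge date whose meaning differs between two SAP sections. If the wrong date is used, ward deaths could be reported as PICU deaths.

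**Working it through.** **1. Expected number of deaths.** The documents give no planned figure for mortality, so the only plan figure to reproduce is the denominator. Protocol 11.3 has 134 per group and 5% dropout: 134 / 0.95 = 141.05, rounded up to 142; 2 × 142 = 284.

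Rates: 1-2% (Protocol 10.2.3) and 1.75% (Protocol 3.2). Expected deaths = 284 × rate:
- 1%: 2.84
- 1.75%: 4.97
- 2%: 5.68

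**2. How many would be counted under the written window.** Let s be the share of deaths that occur in PICU. The documents do not give s; 50% to 90% is an assumption. Counted deaths = 284 × rate × (1 − s). Chance of an empty table = (1 − rate × (1 − s))^284.

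| Rate | All deaths | Counted, s = 50% | Counted, s = 90% | Chance of no event, s = 50% to 90% |
|---|---|---|---|---|
| 1% | 2.84 | 1.42 | 0.28 | 24% to 75% |
| 1.75% | 4.97 | 2.49 | 0.50 | 8% to 61% |
| 2% | 5.68 | 2.84 | 0.57 | 6% to 57% |

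**3. The denominator.** There are two ways to handle infants who died in PICU:
- *Kept as non-events.* The result is post-PICU deaths over all randomised infants. The randomised comparison is preserved, but dead infants sit in the column for no death and the label is wrong.
- *Dropped.* The result is post-PICU deaths over infants who left PICU alive. This conditions on a post-randomisation event.

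The listed outcome is all deaths to day 90 over all randomised infants with known status. Neither option gives that. SAP 17.5 asks for the intention-to-treat principle, which favours the first option, but 17.5.6 does not say so.

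**4. The discharge variable.**
- SAP 17.5.5.1: PDA90DTD is PICU discharge; blank means the death was in PICU.
- SAP 17.4.8.1: PDA90DTD is hospital discharge; PDAISDTD is PICU discharge.

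Both labels cannot be right. SAP 17.5.5.1 says that a completed date places the death in hospital or after hospital discharge, so a PICU discharge date is what the rule needs. Suppose 17.4.8.1 has the correct labels and the hospital discharge date is left blank when an infant dies on the ward. An invented example with 5 deaths (3 in PICU, 1 on the ward, 1 after hospital discharge) then gives:

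| | Safety Outcome 5 | Safety Outcome 6 |
|---|---|---|
| As written | 3 + 1 = 4 | 1 |
| PICU discharge date used, deaths counted from randomisation | 3 | 5 |

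If instead 17.5.5.1 has the correct label, the classification of deaths works as intended and the error lies in the hospital-stay derivation.

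**5. Two details of the derivation.** DNBTBAC covers deaths up to completion of the day-90 form, so a death after day 90 has to be excluded by date. A footnote to 17.4.8.1 says that death is recorded as a date without a time, so a death on the day of PICU discharge needs a stated rule.

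**The case against.** The strongest reply is that Safety Outcomes 5 and 6 are adjacent windows that together cover randomisation to day 90, and Protocol Table 1 sets them out the same way. A reader might infer from the restricted window that PICU deaths vanish from the report. They do not: Safety Outcome 5 gives them by arm with a relative risk, and a misplaced ward death moves between the two outcomes without changing their sum. That part of the reply stands. It does not rescue the listed outcome, because no planned table, test or relative risk adds the two. The serious adverse event tables do not fill the gap either. SAP 20.1 presents them by treatment received, and Protocol 10.2.3 records the condition that led to death as the event, not the death itself.

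A reader might also infer that the trial's main mortality result is wrong. Neither document ranks Safety Outcome 6 above Safety Outcome 5. Nor does every handling of PICU deaths condition on surviving PICU; only dropping them does.

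It is tempting to state that the SAP uses the hospital-discharge variable to identify PICU deaths. The documents show two conflicting labels. The separate naming of PDAISDTD makes 17.4.8.1 the likelier to be correct, but the annotated CRF is not available to confirm it.

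On size, the 1.75% describes infants admitted to English PICUs with bronchiolitis. BESS excludes major congenital anomalies, neuromuscular disease and futility, so 5 deaths may be too many. With 3 to 6 deaths, no between-arm test says much under either definition.

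Finally, the protocol supplied has an amendment log ending at version 2.0, while the SAP cites versions 3.0 and 6.0. Table 1 may have changed since.

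**Conclusion.** The point holds. The outcome named in both lists and the analysis specified for it are different quantities, and a literal reading of the SAP yields a wrong figure under the all-cause label. About 3 to 6 deaths are expected in 284 infants. If 50-90% occur in PICU, which is an assumption, about 0.5 to 2.5 of 5 deaths would be counted, with an 8% to 61% chance that the table has no event at all. A reader might infer that the reported mortality would be zero in both arms; that needs every death to occur in PICU, which the documents do not say.

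The label conflict over PDA90DTD is real, but its direction is unconfirmed. The ward-death error follows only if 17.4.8.1 is right and the hospital discharge date is blank for infants who die on the ward.

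What is affected is the correctness of a named safety outcome. The primary outcome, sample size and data collection are untouched.

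**What to change.** 1. **SAP 17.5.6 and 17.5.6.2.** Define the outcome as any death from randomisation to day 90, using DNBTBAC with the date of death (DNBDIDD) and excluding deaths dated after day 90. The denominator is all randomised infants with known day-90 status, by allocated arm. Keep Safety Outcome 5 as a separate result.
2. **Protocol Table 1.** Change the window for all-cause mortality to match, after checking what the current protocol version says.
3. **SAP 17.5.5.1 and 17.4.8.1.** Check PDA90DTD and PDAISDTD against the annotated CRF and correct whichever section is wrong. Classify a PICU death by comparing the date of death with the confirmed PICU discharge date (PDAISDTD under 17.4.8.1), instead of inferring it from a blank field. State how a death on the day of PICU discharge is classified.

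The cost is a few sentences in the SAP, one variable reference and one table cell. Vital status and date of death are already on the Day 90 Status CRF. The change should be made before the analysis code is finalised, so that the trial statistician and the independent programmer work from the same definition.
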